10.3.2 Distribution of Adverse Event Reports

CTEP-AERS is programmed for automatic electronic distribution of reports to the following individuals: Principal Investigator and Adverse Event Coordinator(s) (if applicable) of the Corresponding Organization or Lead Organization, the local treating physician, and the Reporter and Submitter. CTEP-AERS provides a copy feature for other e-mail recipients.

10.3.3 Expedited Reporting Guidelines

Use the NCI protocol number and the protocol-specific patient ID assigned during trial registration on all reports.

Note: A death on study requires both routine and expedited reporting, regardless of causality. Attribution to treatment or other cause must be provided.

Death due to progressive disease should be reported as Grade 5 “Disease progression” in the system organ class (SOC) “General disorders and administration site conditions.” Evidence that the death was a manifestation of underlying disease (e.g., radiological changes suggesting tumor growth or progression; clinical deterioration associated with a disease process) should be submitted.

Late Phase 2 and Phase 3 Studies: Expedited Reporting Requirements for Adverse Events that Occur on Studies under an IND/IDE within 30 Days of the Last Administration of the Investigational Agent/Intervention^{1,2}

FDA REPORTING REQUIREMENTS FOR SERIOUS ADVERSE EVENTS (21 CFR Part 312)

NOTE: Investigators **MUST** immediately report to the sponsor (NCI) **ANY** SAEs, whether or not they are considered related to the investigational agent(s)/intervention (21 CFR 312.64).

An AE is considered serious if it results in **ANY** of the following outcomes:

- 1) Death
- 2) A life-threatening AE
- 3) An AE that results in inpatient hospitalization or prolongation of existing hospitalization for ≥ 24 hours
- 4) A persistent or significant incapacity or substantial disruption of the ability to conduct normal life functions
- 5) A congenital anomaly/birth defect.
- 6) Important Medical Events (IME) that may not result in death, be life threatening, or require hospitalization may be considered serious when, based upon medical judgment, they may jeopardize the patient or subject and may require medical or surgical intervention to prevent one of the outcomes listed in this definition. (FDA, 21 CFR 312.32; ICH E2A and ICH E6).

ALL SAEs that meet the above criteria **MUST** be immediately reported to the NCI via CTEP-AERS within the timeframes detailed in the table below.

Grade 1-3 Timeframes	Grade 4-5 Timeframes
24-Hour notification, 10 Calendar Days	24-Hour notification, 5 Calendar Days

NOTE: Protocol-specific exceptions to expedited reporting of SAEs are found in the Specific Protocol Exceptions to Expedited Reporting (SPEER) portion of the CAEPR.

Expedited AE reporting timeframes are defined as:

- “24-Hour notification, 5 Calendar Days” - The SAE must initially be reported via CTEP-AERS within 24 hours of learning of the SAE, followed by a complete expedited report within 5 calendar days of the initial 24-hour report.
- “24-Hour notification, 10 Calendar Days” - The SAE must initially be reported via CTEP-AERS within 24 hours of learning of the SAE, followed by a complete expedited report within 10 calendar days of the initial 24-hour report.

¹SAEs that occur more than 30 days after the last administration of investigational agent/intervention and have an attribution of possible, probable, or definite require reporting as follows:

Expedited 24-Hour notifications are required for all SAEs followed by a complete report

- Within 5 calendar days for Grade 4-5 SAEs
- Within 10 calendar days for Grade 1-3 SAEs

²For studies using nuclear medicine or molecular imaging IND agents (NM, SPECT, or PET), the SAE reporting period is limited to 10 radioactive half-lives, rounded UP to the nearest whole day, after the agent/intervention was last administered. Footnote “1” above applies after this reporting period.

10.3.4 Additional Protocol-Specific Expedited Adverse Event Reporting Exclusions N/A

10.4 Routine Adverse Event Reporting

All Adverse Events **must** be reported in routine study data submissions. **AEs reported expeditiously through CTEP-AERS must also be reported in routine study data submissions.**

Adverse event data collection and reporting, which are required as part of every clinical trial, are done to ensure the safety of patients enrolled in the studies as well as those who will enroll in future studies using similar agents. AEs are reported in a routine manner at scheduled times during the trial using Medidata Rave. For this trial the Adverse Event CRF is used for routine AE reporting in Rave.

10.5 Pregnancy

Although not an adverse event in and of itself, pregnancy as well as its outcome must be documented via **CTEP-AERS**. In addition, the ***Pregnancy Information Form*** included within the NCI Guidelines for Adverse Event Reporting Requirements must be completed and submitted to CTEP. Any pregnancy occurring in a patient or patient's partner from the time of consent to 90 days after the last dose of study drug must be reported and then followed for outcome. Newborn infants should be followed until 30 days old. Please see the "NCI Guidelines for Investigators: Adverse Event Reporting Requirements for DCTD (CTEP and CIP) and DCP INDs and IDEs" (at http://ctep.cancer.gov/protocolDevelopment/adverse_effects.htm) for more details on how to report pregnancy and its outcome to CTEP.

10.6 Secondary Malignancy

A *secondary malignancy* is a cancer caused by treatment for a previous malignancy (e.g., treatment with investigational agent/intervention, radiation or chemotherapy). A secondary malignancy is not considered a metastasis of the initial neoplasm.

CTEP requires all secondary malignancies that occur following treatment with an agent under an NCI IND/IDE be reported expeditiously via CTEP-AERS. Three options are available to describe the event:

- Leukemia secondary to oncology chemotherapy (e.g., acute myelocytic leukemia [AML])
- Myelodysplastic syndrome (MDS)
- Treatment-related secondary malignancy

Any malignancy possibly related to cancer treatment (including AML/MDS) should also be reported via the routine reporting mechanisms outlined in each protocol.

10.7 Second Malignancy

A second malignancy is one unrelated to the treatment of a prior malignancy (and is **NOT** a metastasis from the initial malignancy). Second malignancies require **ONLY** routine AE reporting unless otherwise specified.

11. STUDY CALENDAR

Cycles	Screening	Cycle 1				Cycle 2				Cycle 3 Onward ¹⁴	EOT	FU/EOS ¹⁵
Days	w/in-28d	1	8	15	22	1	8	15	22	1		Every 3 Months
Window		-3d	± 3d	± 3d	± 3d	± 3d	± 3d	± 3d	± 3d	± 3d	± 3d	± 14d
Informed consent	X											
Demographics	X											
Medical history	X											
Concurrent meds	X	X-----X										
Adverse event evaluation		X-----X										
Physical exam ¹	X	X		X		X		X		X	X	
Performance status (PS) ¹	X	X		X		X		X		X	X	
Vital signs ¹	X	X		X		X		X		X	X	
Weight ¹	X	X		X		X		X		X	X	
Height ¹	X											
Pregnancy Test (B-HCG) ²	X					X				X	X	
Hematology: CBC w/diff, plts ³	X	X	X	X	X	X	X	X	X	X	X	
Coagulation: PT/PTT/INR ¹¹	X				X						X	
Serum chemistry ^{3, 4}	X	X	X	X	X	X	X	X	X	X	X	
Urinalysis ^{3, 5}	X					As clinically indicated						
12-Lead EKG ⁶	X					As clinically indicated						
Radiologic evaluation ⁷ (CT, MRI or PET/ CT)	X									X	X	
Tumor measurements ⁸	X									X	X	
Tumor-specific markers, such as CA19-9, CA-125, CEA, PSA etc. ⁹	X									X	X	
Whole blood for oncometabolomics ¹⁰	X			X	X							
Whole blood for pharmacokinetics (PK) ¹⁰		X		X								
Whole blood for exploratory genetic biomarkers ¹¹	X				X				X		X	
Tumor Biopsy ¹²	X				X						X	
Study Drug: Telaglenastat (CB-839) HCl ¹³		X -----X										
Survival ¹⁴												X

Footnote:

- Physical exam, PS, Vital sign and weight will be performed at Screening, C1-2 D1 and 15, C3 onward D1 and at End of Treatment (EOT). Height will be done at screening.
- Required of all females of child-bearing potential. Screening serum pregnancy test must occur within 3 days prior to C1D1. Urine pregnancy tests will be performed on D1 of every cycle.

3. Does not need to be repeated if the Screening sample was obtained within 3 days prior to C1D1 unless a clinically significant change is indicated.
4. Albumin, alkaline phosphatase, total bilirubin, bicarbonate, BUN, calcium, chloride, creatinine, glucose, LDH, phosphorus, potassium, total protein, SGOT [AST], SGPT [ALT], sodium. Serum chemistry should be determined at the times indicated.
5. All patients with treatment-emergent proteinuria that is $> 2+$ on urine dipstick are required to have a quantitative urine protein evaluation on a random sample and a calculation of the urine protein/urine creatinine ratio. If the results demonstrate nephrotic range proteinuria, a 24-hr total urine protein evaluation should be performed.
6. 12-Lead EKG (single) will be performed at screening and as clinically indicated.
7. Radiologic evaluation (CT or MRI or PET-CT) will be performed at screening within 28 days prior to C1D1, every 2 cycles (8 weeks), ± 7 days, for the first 13 cycles, then every 3 cycles (12 weeks) ± 7 days and EOT.
8. Tumor measurement: Per RECIST v1.1 for solid tumors and per Modified RECIST (Byrne and Nowak 2004) for pleural mesothelioma. Tumor measurements are repeated every 2 cycles (every 8 weeks) ± 7 days, for the first 13 cycles, then every 3 cycles (12 weeks) ± 7 days and EOT. Documentation (radiologic) must be provided for patients removed from study for progressive disease.
9. Tumor-specific markers, such as CA19-9, CA-125, CEA, PSA, etc. will be tested at the time with radiologic evaluation.
10. Whole blood sample for oncometabolomics and pharmacokinetics will be collected on Day 1 and Day 15 prior to drug administration and after drug administration at 0.5, 1, 2, 4, and 8 hours. In addition, oncometabolomics will be collected on Week 4 (C1D22) post Telaglenastat (CB-839) HCl dose. All "prior to drug administration" samples should be collected after at least 8 hours of fasting (the patient must not eat or drink anything but water). All "after drug administration" samples should be collected after patients are dosed with Telaglenastat (CB-839) HCl immediately after a meal.
11. Optional whole blood sample for exploratory genetic and biomarker testing for cfDNA and WES/RNASeq will be collected at screening, at C1D22, C2D22 and disease progression (EOT) for patients who are consented for such analysis under fasting conditions.
12. Tumor Biopsy: Tumor biopsy at screening are required for all patients for exploratory analyses. In addition, archival tissue samples will be collected if available. Optional on-treatment biopsy will be collected on week 4 (C1D22 ± 3 days) and upon disease progression at EOT. Coagulation tests must be performed and evaluated prior to all biopsy procedures. Patients are consented for tumor biopsy.
13. Telaglenastat (CB-839) HCl dose by mouth twice daily, immediately after a meal on continuous dose from day 1 to day 28-day cycle.
Dosing may occur prior to, during, or after the clinic visit, according to the patient's usual administration schedule.
14. For patients with $\geq SD$ for at least 13 cycles who are on a steady dose for ≥ 2 cycles, study assessments may be reduced to every 3 cycles (i.e., at Cycles 16, 19, 22, etc.) and 3 cycles worth of study medication can be provided at clinic visits.
15. FU/EOS = Follow Up/End of Study: Patient will be followed for survival every 3 months (± 14 days after EOT visit. This may be by telephone contact.

28 in a

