In marmoset monkeys receiving up to 125 mg/kg BID of Telaglenastat (CB-839) HCl for 28 days, Telaglenastat (CB-839) HCl was well tolerated with no mortality, nor notable clinical observations (Investigator's Brochure). In sporadic animals receiving the mid- and high-dose, two liver enzymes, γ -glutamyl- transpeptidase and glutamate dehydrogenase, were significantly elevated at sacrifice, while other liver function tests were within normal limits. This correlated with minimal to slight bile duct hyperplasia. These findings were not observed in animals which underwent a 14-day non-dosing recovery period before sacrifice. The Highest Non Severely Toxic Dose was not defined.

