10.1.1 CAEPRs for CTEP IND Agent

10.1.1.1 CAEPR for Telaglenastat (CB-839) HCl (telaglenastat)

Version 2.2, July 21, 2019¹

Adverse Events with Possible Relationship to Telaglenastat (CB-839) HCl (CTCAE 5.0 Term) [n= 161]			Specific Protocol Exceptions to Expedited Reporting (SPEER)
Likely (>20%)	Less Likely (<=20%)	Rare but Serious (<3%)	
BLOOD AND LYMPHATIC SYSTEM DISORDERS			
	Anemia		
EYE DISORDERS			
	Photophobia		
GASTROINTESTINAL DISORDERS			
	Nausea		Nausea (Gr 2)
	Vomiting		
GENERAL DISORDERS AND ADMINISTRATION SITE CONDITIONS			
Fatigue			Fatigue (Gr 2)
INVESTIGATIONS			
	Alanine aminotransferase increased		Alanine aminotransferase increased (Gr 2)
	Alkaline phosphatase increased		
	Aspartate aminotransferase increased		Aspartate aminotransferase increased (Gr 2)
	GGT increased		
	Platelet count decreased		
METABOLISM AND NUTRITION DISORDERS			

Adverse Events with Possible Relationship to Telaglenastat (CB-839) HCl (CTCAE 5.0 Term) [n= 161]			Specific Protocol Exceptions to Expedited Reporting (SPEER)
Likely (>20%)	Less Likely (<=20%)	Rare but Serious (<3%)	
	Anorexia		

¹This table will be updated as the toxicity profile of the agent is revised. Updates will be distributed to all Principal Investigators at the time of revision. The current version can be obtained by contacting [contact]. Your name, the name of the investigator, the protocol and the agent should be included in the e-mail.

Adverse events reported on Telaglenastat (CB-839) HCl trials, but for which there is insufficient evidence to suggest that there was a reasonable possibility that Telaglenastat (CB-839) HCl caused the adverse event:

CARDIAC DISORDERS - Sinus tachycardia

GASTROINTESTINAL DISORDERS - Constipation; Mucositis oral; Oral pain

GENERAL DISORDERS AND ADMINISTRATION SITE CONDITIONS - Death NOS; Fever

INFECTIONS AND INFESTATIONS - Hepatitis viral; Meningitis

INVESTIGATIONS - Blood bilirubin increased; Creatinine increased; Lymphocyte count decreased; Neutrophil count decreased

METABOLISM AND NUTRITION DISORDERS - Hyperglycemia; Hyponatremia; Hypophosphatemia

MUSCULOSKELETAL AND CONNECTIVE TISSUE DISORDERS - Arthralgia; Myositis

NERVOUS SYSTEM DISORDERS - Seizure

RESPIRATORY, THORACIC AND MEDIASTINAL DISORDERS - Dyspnea; Hypoxia

SKIN AND SUBCUTANEOUS TISSUE DISORDERS - Rash maculo-papular

VASCULAR DISORDERS - Hypertension; Hypotension

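### The scheduled chemistry panel omits GGT, an event listed as possibly related to the agent, so any GGT frequency in the toxicity tables could not be read as an incidence

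*Combined protocol and SAP*

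**What the plan says.** Section 11, Study Calendar, footnote 4 defines serum chemistry as: "Albumin, alkaline phosphatase, total bilirubin, bicarbonate, BUN, calcium, chloride, creatinine, glucose, LDH, phosphorus, potassium, total protein, SGOT [AST], SGPT [ALT], sodium". The list is closed, with no wording that lets sites treat it as examples. The footnote adds: "Serum chemistry should be determined at the times indicated". The calendar marks those times as screening, days 1, 8, 15 and 22 of Cycles 1 and 2, day 1 of later cycles, and end of treatment.

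Section 10.1.1.1 (CAEPR) lists "GGT increased" under Investigations, in the column for frequencies up to 20%. The table is headed "Adverse Events with Possible Relationship to Telaglenastat (CB-839) HCl (CTCAE 5.0 Term) [n= 161" (the bracketed figure is the number of patients).

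Section 2.2.2 reports a 28-day marmoset study. In scattered animals at the middle and top doses, gamma-glutamyl transpeptidase and glutamate dehydrogenase "were significantly elevated at sacrifice, while other liver function tests were within normal limits". It continues: "This correlated with minimal to slight bile duct hyperplasia". It then limits the finding: "These findings were not observed in animals which underwent a 14-day non-dosing recovery period before sacrifice".

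Section 9.3 makes safety a secondary endpoint and analyses it by tabulating toxicities. Section 9.4.1 counts every patient as evaluable for toxicity from the first dose.

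**The concern.** The protocol names GGT elevation as something the agent may cause but schedules no test that could show it. The other liver-enzyme events on the same list all have a scheduled test.

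What is at stake is how one line of the safety results can be read. A laboratory event enters a toxicity table only if someone runs the assay. If GGT is measured only when a site chooses to order it, the table mixes patients tested and found normal, patients tested and found abnormal, and patients never tested. A zero in that line would carry no information, and a non-zero figure could not be compared with the ALT, AST or alkaline phosphatase lines beside it. The animal summary adds some interest, because GGT was one of the two enzymes that moved when the other liver tests did not.

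**Working it through.** The plan states no figure to reproduce on this point. The check sets its sections side by side.

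**1. The panel.** Footnote 4 names 16 analytes. Those bearing on the liver are albumin, total protein, LDH, alkaline phosphatase, total bilirubin, AST and ALT. GGT is absent.

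**2. The listed laboratory events against the scheduled tests.**

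| Laboratory event in the CAEPR main table | Scheduled test in Section 11 |
|---|---|
| Anemia | Yes, blood count |
| Platelet count decreased | Yes, blood count |
| ALT increased | Yes, footnote 4 |
| AST increased | Yes, footnote 4 |
| Alkaline phosphatase increased | Yes, footnote 4 |
| GGT increased | None |

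Of the four liver-enzyme terms, three are covered and GGT is the one that is not.

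**3. Other places GGT could be scheduled.** No other calendar row or footnote includes it. The eligibility laboratory criteria (Section 3.1.13) use bilirubin, AST and ALT. The liver rows of the dose-modification guidelines (Section 7) use ALT, AST and bilirubin.

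**4. Sampling opportunities.** Through Cycle 2 the calendar marks 1 (screening) + 4 (Cycle 1) + 4 (Cycle 2) = 9 chemistry visits at most. Footnote 3 lets the Cycle 1 day 1 draw be skipped when the screening sample is recent enough, which leaves 8. Patients who stop early have fewer. Later draws fall on day 1 of subsequent cycles and at end of treatment. GGT is scheduled at none of these, although the sample is already being taken.

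**5. Effect on the safety table.** Let N be the number treated, m the number who happen to have GGT measured on treatment, and x the number with a recorded GGT event.

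- Under Section 9.4.1 the natural denominator is N, giving x/N. This counts the N − m untested patients as event-free, which pulls the figure down.
- With no scheduled screening value, a rise already present before the first dose can be counted in x, which pushes the figure up.
- The alternative, x/m, describes patients selected because someone had a reason to test them, and the plan does not define or collect m.

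The errors run in both directions and their size is unknown, so neither ratio estimates an incidence.

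**The case against.** The best defence is that the CAEPR is a reference list for adverse event reporting and not a monitoring schedule. Nothing requires the chemistry panel to match it. No eligibility rule, dose rule or endpoint uses GGT, so measuring it would change no decision the protocol defines. That is correct, and it makes this a gap in data collection and not a contradiction in the plan.

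Several stronger readings are tempting, and the documents do not support them.

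- *Liver safety is unmonitored.* It is monitored often: ALT, AST, alkaline phosphatase and total bilirubin are due weekly in Cycles 1 and 2 and continue afterwards. Section 10.4 requires all adverse events to be reported, so a GGT rise found off schedule would still be captured.
- *GGT elevation is an established effect of the drug.* The CAEPR heading claims only a possible relationship.
- *The scheduled tests are known to miss the biliary finding.* Section 2.2.2 does not say which other liver tests were normal in the marmosets. The animal change was also sporadic, graded no higher than slight, and absent after 14 days off drug.
- *Scheduled GGT would settle whether the drug affects the bile ducts.* It could not. The trial is single-arm, and Section 3.1.13 admits patients with liver metastases, which can themselves raise GGT.
- *The number of affected patients can be calculated.* The frequency column has a ceiling of 20% and no stated floor. The 108 patients in Section 9.2 are a maximum; under the null, expected enrolment is 4 × 15.7 = 62.8. The monotherapy experience in Section 2.2.5 (161 patients, the number the CAEPR uses) includes 59 treated three times daily while fasted, and Section 6.1.1 reports fewer liver test elevations with food, as used here. Any patient count would be conjecture.

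**Conclusion.** The point holds in a limited form. GGT is a listed, possibly related event with no scheduled measurement, and it is the only one of the four liver-enzyme terms left out. As written, a GGT frequency in the toxicity tables would have no systematic baseline and no defined denominator, so it should not be reported or read as an incidence.

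The effect is confined to one line of a descriptive secondary analysis. The response endpoint, the two-stage rule, its error rates and the routine liver monitoring are untouched. The change is worth making because it is nearly free, not because the trial is unsound without it.

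The conclusion assumes that sites follow footnote 4 as a closed list and that no GGT schedule sits in a part of the protocol not available for this review.

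**What to change.** Add GGT to the analyte list in Study Calendar footnote 4, making 17 analytes. Run it on the chemistry sample already drawn at screening and at each scheduled chemistry visit. In the toxicity tables, report it with its baseline value and the number of patients tested.

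If the sponsor prefers not to collect GGT, a sentence saying why, and that its incidence will not be estimated, would remove the ambiguity in the tables.

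The cost is one assay on an existing tube and one laboratory field in the case report form, with no extra visit or blood draw. The small downside is more low-grade laboratory adverse events to record, some of them due to liver metastases. The change adds a measurement only; no management rule is proposed.

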6.4 Duration of Follow Up

Patients will be followed every 3 months (\pm 14 days after the last administered treatment dose or until death, whichever occurs first. Patients removed from study for unacceptable adverse event(s) will be followed until resolution or stabilization of the adverse event.

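### No scheduled safety contact is tied to the 30-day reporting window after the last dose, and the timing of the end-of-treatment visit is undefined

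*Combined protocol and SAP*

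**What the plan says.** Section 10.3.3 requires expedited reporting of serious adverse events that occur "within 30 Days of the Last Administration of the Investigational Agent/Intervention", whether or not they are thought related. Later serious events stay reportable if they are at least possibly related.

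In the Section 11 calendar the last column with clinical assessments is EOT. Its day cell is blank and its window is ±3 days; nothing says how long after the last dose it falls. The next column is FU/EOS, every 3 months ±14 days. Footnote 15 describes that contact: "Patient will be followed for survival every 3 months", counted from the EOT visit, and "This may be by telephone contact". The row "Adverse event evaluation" is a bar that starts on treatment. Where it ends cannot be read in the available copy of the table.

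Section 6.4, like Table 2 in Section 6.1, gives the same 3-month interval but counts it from a different start: "14 days after the last administered treatment dose". It makes one special provision: "Patients removed from study for unacceptable adverse event(s) will be followed until resolution or stabilization of the adverse event".

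Section 9.3 plans toxicity tables broken down by cohort, kind of event, grade and attribution. Section 9.4.1 says when a patient becomes evaluable for toxicity (first treatment) but not when collection stops.

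**The concern.** A reporting window finds events only if someone asks about them or someone volunteers them. The plan sets a 30-day window for serious events but schedules no enquiry tied to its end. The expedited clock in Section 10.3.3 starts when the site learns of the event, so detection after EOT is passive unless a contact is planned.

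Safety is a secondary objective (Section 1.2). Patients who stop for progression or other non-toxicity reasons have no required adverse-event follow-up after EOT. Sites may therefore differ in how long they look, and with no stated cutoff the toxicity tables may mix different lengths of post-treatment observation. If late events are missed, the tables would read low.

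**Working it through.** The plan states no figure for the length of this gap, so none can be reproduced. The check sets obligation against schedule, then counts days.

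**1. Obligation against schedule**

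| Item | Source | Content |
|---|---|---|
| Serious-event window | 10.3.3 | 30 days after last dose, any cause |
| Last clinical visit | 11 | EOT, ±3 days, no anchor to last dose |
| Next contact | 11, footnote 15 | survival, 3 months ±14 days after EOT, telephone allowed |
| Same interval elsewhere | 6.1 Table 2; 6.4 | 3 months ±14 days after last dose |
| Follow-up of known events | 6.4 | only patients removed for unacceptable adverse events |

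None of Sections 6.1, 6.4, 10 or 11 adds a safety visit or call between EOT and the first 3-monthly contact.

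**2. When the first follow-up contact falls**

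Three months = 3 × 365.25 / 12 = 91.3 days. The window is 91.3 − 14 = 77.3 to 91.3 + 14 = 105.3 days.

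- Clock from the last dose (6.1, 6.4): the contact comes 77.3 − 30 = 47 to 105.3 − 30 = 75 days after the 30-day window has closed.
- Clock from EOT (11): with EOT on day *e* after the last dose, the contact comes on day *e* + 77.3 to *e* + 105.3. Even with *e* = −3 the earliest is day 74.3, which is 44 days after the window has closed.

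Under either clock the follow-up contact falls outside the 30-day window.

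**3. How much of the window has no scheduled contact**

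Days from EOT to day 30 = 30 − *e*. The plan does not give *e*, so a range is shown.

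| EOT, day relative to last dose (assumed) | Days from EOT to day 30 |
|---|---|
| −3 | 33 |
| 0 | 30 |
| +3 | 27 |
| +7 | 23 |
| +14 | 16 |
| +28 | 2 |

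The 33 includes three days before the last dose. The 30-day window itself cannot lose more than 30 days.

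**4. How many patients**

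The maximum is 4 × 27 = 108 (Section 9.2). If every cohort is null (response rate 0.05), the probability of stopping at stage 1 is 0.95^9 = 0.630. Expected enrolment per cohort is then 9 + 18 × (1 − 0.630) = 15.7. Both match Section 9.1 (63% and 15.7). Across four cohorts that is 4 × 15.7 = 62.8, about 63.

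**The case against.** The case for leaving the plan alone has real substance.

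- **A reporting rule is not an ascertainment schedule.** Section 10.3.3 says which events must be reported and does not promise active enquiry to day 30. Nothing is contradicted. This stands: the point is a design improvement, not the correction of an error.
- **Other routes exist.** A reader might infer that late toxicity in every patient is found only by chance. The documents do not support that. Section 6.4 follows patients removed for unacceptable adverse events to resolution or stabilization. Sites must report any serious event they learn of, survival contacts find deaths, and pregnancies are reportable to 90 days (Section 10.5). What remains is new non-fatal events, mainly in patients who stop for other reasons.
- **The adverse-event bar may extend further.** A reader might also infer that nobody asks about adverse events until after the 3-month contact. The bar in the calendar could run into the FU/EOS column, and Sections 6.1 and 6.4 do not limit follow-up to survival. Footnote 15 points to survival only, but the question is open. Even on the favourable reading, the first enquiry after EOT would be at the 3-month contact, weeks after day 30.
- **EOT may be late enough.** At day 28 only 2 days are left. Nothing in the plan requires that timing.
- **Late events may be few.** The half-life is about 4 hours (Section 2.2.4), the inhibitor is reversible (Section 8.1.1), and adverse events on the twice-daily schedule were typically grade 1 or 2 and reversible (Section 2.2.5). EOT includes examination, hematology and chemistry. The trial has one arm, so no treatment comparison is biased. This limits the likely harm but does not replace the contact: the serious-event window applies regardless of cause.

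**Conclusion.** The point holds in limited form. No scheduled safety contact is tied to the 30-day window, EOT is not anchored to the last dose, and the 3-month clock has two different starts. With EOT assumed between 3 days before and 28 days after the last dose, 33 down to 2 days from EOT to day 30 have no scheduled contact. The next one is about 77 to 105 days after EOT or the last dose, depending on which section is followed. New non-fatal late events in patients who stop for reasons other than toxicity therefore depend on spontaneous report or routine care.

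A reader might go on to conclude that the trial's toxicity is understated. That is the likely direction, but the documents give no rate of late events, so neither its presence nor its size can be shown. This is a cheap improvement to safety collection; it does not affect the primary endpoint.

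**What to change.** 1. Add one adverse-event contact to the Section 11 calendar at 30 (+7) days after the last dose, by telephone if no visit is planned, to record new and ongoing events.
2. Define the EOT visit relative to the last dose, and state where the adverse-event evaluation row ends.
3. Reconcile the start of the 3-month follow-up clock between Sections 6.1 and 6.4 (last dose) and Section 11 footnote 15 (EOT visit).
4. State in Section 9.3 that the toxicity tables cover events up to 30 days after the last dose.

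The cost is one call per treated patient and a calendar line, with no added procedure: at most about 108 calls, or about 63 expected if all four cohorts are null.
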